7.2.3 Sensitivity Analysis

The impact of missing data on the primary safety and efficacy analyses will be further explored as sensitivity analyses using observed data as well as last observation carried forward (LOCF).

7.3 Interim Analysis

An interim analysis after 60% of enrollment will be conducted. The purpose of the interim analysis is a blinded sample size reassessment using the approach by Friede and Kieser¹¹ for an absolute difference in means which is based on the observed one-sample standard deviation calculated from the pooled data across treatment groups (described in more detail, below). This blinded sample size reassessment will be carried out by an independent statistician (who otherwise is not involved in the study conduct) using the 8 week measurements of the pre-dialysis serum albumin levels after 100 total patients have

been enrolled (assuming 15% drop out, this corresponds to 84 evaluable patients). In case the observed pooled standard deviation at 8 weeks is larger than the assumed standard deviation of 3.7, the method will require an increase in overall sample size in order to maintain an overall power of 80%. If the observed standard deviation is smaller than or equal to the assumed standard deviation of 3.7, the overall sample size will be kept at 166.

We consider a two-sample situation comparing a test treatment (T) with a control (C). Suppose that $X_{T1}, X_{T2}, ...$ and $X_{C1}, X_{C2}, ...$ are series of independent normal observations with means μ_T and μ_C , respectively, and common unknown variance σ^2 .

If the margin δ^{D} denotes the defined range for the difference of means, the corresponding non-inferiority test problem can be formulated as follow:

 $H_0: \mu_{\mathrm{T}} - \mu_{\mathrm{C}} \leq \delta^{\mathrm{D}}$ versus $H_1: \mu_{\mathrm{T}} - \mu_{\mathrm{C}} > \delta^{\mathrm{D}}$

Here we denote σ^2 as the pooled variance estimate. The non-inferiority hypothesis H_0 can be rejected at level α . The total required sample size for the rejection of H_1 with power 1 – β at the specified alternative $\theta_D^* = \mu_T - \mu_C$ is approximated by

$$N_D = 4 \frac{(z_{1-\alpha} + z_{1-\beta})^2}{(\theta_D^* - \delta^D)^2} \sigma^2$$

where z_{1-prob} denotes the value exceeded by a standard normal random variable with probability *prob*. (In this study, $\alpha = 0.025$ and $\beta = 0.2$.) The required sample size for the non-inferiority test problem H_0 versus H_1 is for $\theta_D^* = 0$ given by the N_D . Then this number should be first rounded up to the upper even integer limit considering it will be a total sample size of two groups (per-protocol set). Later, inflate it by 15% drop out rate and round up to upper even integer limit again. The final number will be recognized as the new total sample size (full analysis set). If the observed pooled SD is smaller than 3.7, the re-estimated sample size will be smaller than 140 (PPS) and 166 (FAS). In these cases, the overall sample size will remain at 166 (FAS). There will be no decrease of sample size.

| Table Number | Table Name |
|--------------|--|
| 14.1.1 | Subject Disposition |
| 14.2.2 | 8 Week Albumin Overall Standard Deviation and Re-Estimated Sample Size Estimate |

Table 3. List of Tables and Listings for Interim Analysis

| Listing Number | Listing Name | | | |
|----------------|--|--|--|--|
| 16.2.1.1 | Patient Disposition | | | |
| 16.2.1.2 | Inclusion and Exclusion Criteria | | | |
| 16.2.1.3 | Reasons for Withdrawal Prior to 8-week Study Treatment | | | |
| 16.2.2 | Protocol Deviations | | | |
| 16.2.8.1 | 16.2.8.1 Albumin Measurements | | | |

7.4 Pooling Strategy for Study Sites

Data will be pooled across all study sites unless indicated otherwise. Protocol deviations and treatment compliance will be presented in total across all study sites and split by study sites.

7.5 Visit Windows/Unscheduled Visits

For tabulation, values will be summarized according to the planned time point as recorded in the eCRF. Data recorded at unscheduled visits will only be presented in listings.

7.6 Calculation of Total Scores for Patient Reported Outcome Measures

7.6.1 Kidney Disease and Quality of Life (KDQOL-36)

The KDQOL-36 questionnaire is a 36-question survey that assesses subjects' quality of life and general well-being as it relates to their kidney disease.

The scores in each question of the KDQOL-36 scale do not all point in the same direction. For some questions a higher score indicates a better quality of life, while for other questions a higher score indicates poorer quality of life. Therefore, to calculate total scores, the direction of the values for each question must be recoded prior to calculating the total score.

As such, the SAS procedure developed by the KDQOL Working Grouptzer¹², will be used to convert the raw scores to recoded scores and individual scale scores. A description of the recoding procedure is summarized in Table 4.

| Table 4: Kidney Diesase and Quality of Life | | | | | | | |
|---|----------------------------|---------------------|--|--|--|--|--|
| Item Number | Original Response Category | To Recoded Value Of | | | | | |
| 1, 8, 17 – 36 ^a | 1 | 100 | | | | | |
| | 2 | 75 | | | | | |

| | 3 | 50 | | | |
|---|---|-----|--|--|--|
| | 4 | 25 | | | |
| | 5 | 0 | | | |
| 2-3 | 1 | 0 | | | |
| | 2 | 50 | | | |
| | 3 | 100 | | | |
| 4-7 | 1 | 0 | | | |
| | 2 | 100 | | | |
| 9-10 | 1 | 100 | | | |
| | 2 | 80 | | | |
| | 3 | 60 | | | |
| | 4 | 40 | | | |
| | 5 | 20 | | | |
| | 6 | 0 | | | |
| 11 | 1 | 0 | | | |
| | 2 | 20 | | | |
| | 3 | 40 | | | |
| | 4 | 60 | | | |
| | 5 | 80 | | | |
| | 6 | 100 | | | |
| 12 - 16 | 1 | 0 | | | |
| | 2 | 25 | | | |
| | 3 | 50 | | | |
| | 4 | 75 | | | |
| | 5 | 100 | | | |
| The answer for Question 28 will come from Question 28a on the survey (for hemodialysis patients | | | | | |

only). Question 28b will not be included in the calculation since it only applies to peritoneal dialysis patients. If both Question 28a and 28b are populated, then the more severe score will be used.

The recoded values will be subsequently classified as indicated in Table 5 to create the individual scale scores.

| Scale | Combination ^a of Individual Questions | | |
|---------------------------------|--|--|--|
| SF-12 Physical Health Composite | 1 - 12 | | |
| SF-12 Mental Health Composite | | | |
| Burden of Kidney Disease | 13 - 16 | | |
| Symptom, Problem List | 17 – 28b | | |
| Effects of Kidney Disease | 29 - 36 | | |

^a For 'Burden of Kidney Disease', 'Symptom, Problem List', and 'Effects of Kidney Disease' the individual question scores will be averaged. For the remaining scale items, the questions will be combined into the corresponding scores as indicated by the SAS procedure developed by the KDQOL working group^{12.}

Calculation of an overall total score is not recommended by the KDQOL Working Group.¹³ Instead, the results of the questionnaire are best interpreted by using the domain scores described above. As such, these domain scores will be used for analyses instead of a total score.

Since the individual scale scores are calculated as an average or combination of the contributing questions, if an answer to a question is missing then the domain score will still be calculated. If all the questions contributing to the individual scale score are missing, then the individual scale score will be missing.

Question 28 is composed of two parts: 28a is only to be answered by patients on hemodialysis and 28b is only to be answered by patients on peritoneal dialysis. In some cases, patients give answers to both items. If this is the case, the most extreme response of the two will be taken and used in the computation of the domain score as described above.

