4.2 Inclusion Criteria

All of the following criteria must be met for the patient to be enrolled in this study.

1. ESRD patients age 22 and older, or between ages 18 and 21 with a weight ≥ 40 kg.
2. Clinically stable as judged by the treating physician and as demonstrated by stable medical history for 30 days prior to enrollment, physical examination, and laboratory testing.
3. Hemodialysis therapy with high-flux dialyzers for at least 3 months immediately prior to study enrollment and expected to survive for the next 12 months.
4. Expected to maintain an acceptable urea clearance (Kt/V) with a dialyzer of an approximate surface area of 1.7 m^2 .
5. Currently being dialyzed at an in-center setting, on a schedule of 3 times per week.
6. Able to give informed consent after an explanation of the proposed study, and who are willing to comply with the study requirements for therapy during the entire study treatment period.
7. Have a stable functioning vascular access (arteriovenous fistula, graft, or dual-lumen tunneled catheter); stable access will be confirmed by observed Kt/V ≥ 1.2 for past 2 measurements and/or achievement of within 15% the prescribed blood flow rate over 3 treatments prior to study entry.

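### SAP 7.6.1 is inconsistent on KDQOL-36 item 28 and lets the peritoneal-dialysis part (28b) override the hemodialysis part (28a) in a hemodialysis-only trial

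*SAP*

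**What the plan says.** SAP 7.6.1 deals with item 28 in three places.

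- **Note to Table 4.** It begins with a default: "The answer for Question 28 will come from Question 28a on the survey". It then excludes the other part and gives the reason: "Question 28b will not be included in the calculation since it only applies to peritoneal dialysis patients". The sentence after that reads: "If both Question 28a and 28b are populated, then the more severe score will be used".
- **Table 5.** The Symptom/Problem scale is given as items 17 to 28b.
- **Closing paragraph of 7.6.1.** It says who should answer which part: "28a is only to be answered by patients on hemodialysis and 28b is only to be answered by patients on peritoneal dialysis". It notes that some patients answer both, and for them "the most extreme response of the two will be taken and used in the computation of the domain score as described above".

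On the population, Protocol 4.2 requires: "Currently being dialyzed at an in-center setting, on a schedule of 3 times per week". Protocol 4.3 excludes patients who plan to move to peritoneal dialysis within nine months. Protocol 4.5 lists a switch to peritoneal dialysis among the reasons for withdrawal.

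The domain scores, not a total score, are analysed. SAP 13 fits an MMRM to the change from the first treatment day at weeks 12 and 24, as an exploratory analysis.

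**The concern.** The reason given for leaving out 28b is that it does not apply to hemodialysis patients. That reason is just as good when a hemodialysis patient has answered both parts. Yet in exactly that case the SAP lets 28b replace 28a whenever 28b is worse. No patient on study treatment should have a valid answer to 28b, so the rule can only bring in an answer given in error.

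The wording also varies. The Table 4 note refers to severity. The closing paragraph refers to the most extreme response, which does not by itself name a direction. The Table 5 range could be read as averaging 28a and 28b as separate items. Two programmers working from 7.6.1 could therefore compute different scores from the same form.

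What is at stake is the Symptom/Problem domain score. A patient who answers 28b at one visit and not at another can show a change in symptoms that comes only from how the form was filled in.

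**Working it through.** The plan states no figure on this point, so there is none to reproduce. The check compares the score under the rule with the score from 28a alone.

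**Inputs (all from SAP 7.6.1)**

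- Recoding in Table 4 for items 17 to 36: responses 1, 2, 3, 4, 5 become 100, 75, 50, 25, 0. A more severe answer gives a lower score, in steps of 25.
- The Symptom/Problem score is the mean of its recoded items. Items 17 to 28, with item 28 counted once, make 28 - 17 + 1 = 12 items.
- A domain is scored as long as at least one of its items is answered.

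**Shift in the score at one visit**

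With *a* and *b* the recoded values of 28a and 28b, and all 12 items answered:

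shift = [min(*a*, *b*) - *a*] / 12

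- *b* one category worse than *a*: -25/12 = -2.08 points.
- *b* four categories worse (*a* = 100, *b* = 0): -100/12 = -8.33 points.
- *b* equal to or better than *a*: 0.

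Of the 5 × 5 = 25 possible response pairs, 10 lower the score, 15 leave it unchanged and none raises it.

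The shift grows when other items are missing. With only five other items answered, the largest shift is -100/6 = -16.7 points.

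**Shift in change from the first treatment day**

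With all 12 items answered at both visits:

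error in change = shift at week 12 or 24 - shift at first treatment day

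Each term lies between -8.33 and 0, so the error in one patient's change lies between -8.33 and +8.33. If 28b is answered, and is worse, only on the first treatment day, later change looks too good. If this happens only at a later visit, change looks too bad.

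**Shift in the treatment difference**

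Let *p* be the proportion of forms with both parts answered and 28b worse, and *D* the mean gap on those forms. The mean level at a visit falls by *pD*/12. The documents give neither *p* nor *D*. As an assumption only:

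- *p* = 1%, *D* = 25: 0.01 × 25/12 = 0.02 points.
- *p* = 20%, *D* = 100: 0.20 × 100/12 = 1.67 points.

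This is a shift in level at one visit. If *pD* is the same at both visits, it cancels from the mean change. If *pD* moves over time equally in both arms, it cancels from the treatment difference. A bias in the comparison needs *pD* to change differently by arm, and nothing in the documents points to that.

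**Literal reading of Table 5**

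If 28a and 28b were both averaged, there would be 13 items. Suppose the other 11 items average 75 (assumed), so that their sum is 825:

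- *a* = 100, *b* = 0: 925/13 - 925/12 = 71.15 - 77.08 = -5.93 points against scoring 28a alone.
- *a* = 0, *b* = 100: 925/13 - 825/12 = 71.15 - 68.75 = +2.40 points.

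This third reading gives different scores again, and they can move in either direction.

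**The case against.** The Table 4 note can be read as a default followed by an exception: use 28a, but if both parts are answered, take the worse. The closing paragraph states the same exception. On that reading the case is pre-specified, and calling the text a flat contradiction goes too far. This stands as a reading of the wording. It does not rescue the rule, because the exception still scores an item that the SAP says does not belong to these patients.

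A reader might infer that the rule biases the quality-of-life comparison towards worse symptoms. The documents do not support this. The one-way direction holds for the score at a visit. It does not hold for change from the first treatment day, and the same rule covers both arms and every visit.

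The rule may also come from the cited KDQOL SAS scoring program, to which 7.6.1 assigns the recoding and the scale scores. The documents do not show how that program treats item 28, so scoring 28a alone could depart from it. This stands, and the fix has to allow for it.

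Finally, the problem may be rare. Protocol 6.6 has patients complete the questionnaires on ePRO devices, and nothing says whether the device lets both parts be answered. The SAP does expect that some patients will answer both, but gives no rate. KDQOL-36 is exploratory and lies outside both primary tests and the eight-step secondary hierarchy in SAP 12.3.

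**Conclusion.** The point holds in a limited form. SAP 7.6.1 is inconsistent on item 28, and its stated rule for forms with both parts answered lets an inapplicable answer override the valid one. With 12 items answered, the affected visit score falls by 2.08 points per response category, to a maximum of 8.33, and never rises. For one patient's change from the first treatment day, the error lies between -8.33 and +8.33.

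The sizes rest on the Table 4 recoding, on item 28 counting once, and on complete forms. Missing items make the shift larger. The effect on group means cannot be determined, because the rate of double answers is not given.

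The consequence is avoidable noise and an ambiguous score in an exploratory endpoint. The primary and hierarchical secondary analyses are untouched. This is a minor point, worth making because the correction is nearly free.

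**What to change.** In SAP 7.6.1:

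1. State one rule: item 28 is scored from 28a only, 28b is ignored, and item 28 is missing if 28a is blank.
2. Delete the sentence in the Table 4 note that takes the more severe score, and the matching one in the closing paragraph that takes the most extreme response.
3. Change the Table 5 range for the Symptom/Problem scale to items 17 to 28a.
4. Check that the cited SAS scoring program is run consistently with this rule. If the program itself takes the worse answer, record the departure and report the program's version as a sensitivity analysis.

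The cost is three wording changes, one line of scoring code and possibly a small, documented departure from the cited program.

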7.6.2 Health-Related Quality of Life Questionnaire (EQ-5D-5L)

The 5-level EQ-5D version (EQ-5D-5L) was introduced by the EuroQol Group¹⁴ in 2009 to improve the instrument's sensitivity and to reduce ceiling effects, as compared to the EQ-5D-3L. The EQ-5D-5L essentially consists of 2 pages: the EQ-5D descriptive system and the EQ visual analogue scale (EQ VAS).

The descriptive system comprises five dimensions: mobility, self-care, usual activities, pain/discomfort and anxiety/depression. Each dimension has 5 levels: no problems, slight problems, moderate problems, severe problems and extreme problems. The patient is asked to indicate his/her health state by ticking the box next to the most appropriate statement in each of the five dimensions. This decision results in a 1-digit number that expresses the level selected for that dimension. The digits for the five dimensions can be combined into a 5-digit number that describes the patient's health state.

The EQ VAS records the patient's self-rated health on a vertical visual analogue scale, where the endpoints are labelled 'The best health you can imagine' and 'The worst health you can imagine'. The VAS can be used as a quantitative measure of health outcome that reflect the patient's own judgement. EQ-5D-5L value sets are available for each country that performed a valuation study for the EQ-5D-3L (Table 6). By using the crosswalk link function and the individual responses to the EQ-5D-5L descriptive system, index

values for the EQ-5D-5L can be calculated. Documents containing information on the crosswalk project, tables of values for all 3125 health states and the 'EQ-5D-5LCrosswalk Index Value Calculator' can be downloaded from the EuroQol website.¹⁵

| Variable Name | Self-care | Activity | Pain | Anxiety | State | EQ_VAS ^a |
|-------------------------|---|---|--|---|-------------------------------------|----------------------|
| Variable Description | 1=No problems 2=Slight problems 3=Moderate problems 4=Severe problems 5=Unable to 9=Missing value | 1=No problems 2=Slight problems 3=Moderate problems 4=Severe problems 5=Unable to 9=Missing value | 1=No pain 2=Slight pain 3=Moderate pain 4=Severe pain 5=Extreme pain 9=Missing value | 1=Not anxious 2=Slightly anxious 3=Moderately anxious 4=Severely anxious 5=Extremely anxious 9=Missing value | 5-digit code for EQ- 5D-5L | 999=Missing value |

Table 6: Organizing EQ-5D-5L Data

^a From 'EQ-5D-5LCrosswalk Index Value Calculator' downloaded from the EuroQol website based on values as US location.

7.6.3 Utilization for Medications

All medications should be recorded in the source documents or equivalent. Prior medications, defined as all medications at screening and any ESA taken in the last 30 days before the study begins (ICF), will be recorded on the eCRF. Concomitant medications, including dose, unit, frequency, route of administration, start and stop dates and indication for use, will be recorded on the eCRF throughout the study. Sites will not enter "other" or "prophylaxis" as indications.

Erythropoiesis-stimulating agents are often used to stimulate red blood cell production in dialysis patients. During the course of this study, ESAs should be administered according to each clinic's standard practices, either subcutaneously or intravenously. If administered intravenously, it should be done post-dialysis or in the venous part of the extracorporeal circuit (downstream of the dialyzer).

A treatment medication will be anything given once the patient enters Visit 1.

Medication of erythropoiesis-stimulating agent (ESA), anti-hypertensives, iron and phosphate will be derived from concomitant medication from corresponding categories coded by WHO drug dictionary. Only quantifiable doses and frequencies will be included in analysis. For drugs having "tablet" or "as needed" will only be listed as concomitant mediation. Cumulative dose for every 4 weeks' interval will be standardized by unit; and summarized descriptively (mean, SD, median, min, max) and change form baseline (i.e. cumulative dose from 4 weeks prior to study treatment and before 1st treatment day).

7.7 Other Issues

Not applicable.

8. DEMOGRAPHICS AND BASELINE CHARACTERISTICS

Continuous demographic and baseline characteristics including age, height, screening laboratory tests, screening vital signs and renal medical history will be summarized descriptively by treatment group and overall using sample size (N), mean, SD, minimum and maximum. A t-test or Wilcoxon rank-sum test, as appropriate, will be used to evaluate potential differences in the distribution of the underlying demographic or baseline characteristics between treatment groups.

Categorical demographic and baseline characteristics including gender, race, ethnicity, general medical history and renal medical history will be summarized descriptively by treatment group using frequencies and percentages. Treatment group comparability will be evaluated using Fisher's exact test. Medical history, medical condition or surgery items collected on the eCRF will be coded to the appropriate System Organ Class (SOC) and Preferred Term (PT) using the Medical Dictionary for Regulatory Activities (MedDRA), Version 18 or higher.

Information regarding the type and frequency of dialysis therapy received prior to enrollment in this study, and the type of access will be presented. The information gathered will include mean duration of treatments, blood flow rate (Q_B), dialysate flow rate (Q_D) and the type and mean dosage of heparin, erythropoietin and intravenous iron administered.

Relevant medical history for each patient will be obtained during Screening. Medication history, if applicable, will also be evaluated during the Screening period. Past and present conditions, as well as surgical procedures, will be recorded for the main body systems.

Renal medical history, date and type of first chronic dialysis treatment, date of last transplant (if applicable), date of last transplant failure (HD resumed, if applicable), primary renal disease etiology will also be captured in the eCRF. In addition, all medications being taken at Screening and any ESA taken in the 30 days before screening will be recorded.

9. TREATMENT COMPLIANCE AND EXPOSURE

Each patient should receive 73 study treatments during the study period. Treatment compliance will be assessed by counting the number of scheduled treatments delivered to each patient within the study period. A patient may be withdrawn from the study if more than 3 consecutive treatments with the randomized dialyzer/treatment mode are missed.

The following information on the study dialysis will be tabulated by treatment group and visit and/or provided in a listing.

9.1 Study Treatment Information

- Study treatment date, start/end time (listing only)
- Dialyzer lot number (listing only)
- Actual treatment duration
- Blood flow rate (Q_B)
- Dialysate flow rate (Q_D)
- Ultrafiltration flow rate (Q_{UF})
- Actual total ultrafiltration volume at end of treatment
- Interruptions occurred during the treatment: reason (free text), start/end time for each interruption (listing only)

